6.2. Observational Extension Trial Analysis Set

6.2.1. Extension Enrolled Set

The Extension Enrolled Set (EES) will consist of eligible subjects who consented to participate in the extension portion of the trial. Subjects will be analyzed as initially treated.

6.3. Protocol Deviations

Protocol deviations are defined as instances in which subjects or investigational site study personnel fail to adhere to the protocol requirements (e.g., eligibility criteria, addition or deletion of tests, dosing, duration of treatment, and/or any other aspect of the study design) and the deviation is considered major if the deviation has the potential to impact subject safety or the primary and secondary endpoints of the trial. Deviations are collected in Clinical Trial Management System (CTMS).

This document is confidential.

7. General Aspects for Statistical Analysis

7.1. General Methods

- No formal statistical hypotheses to be tested for the study. 95% confidence interval (CI) and p-value are presented for data nature.
- Unless otherwise specified, summaries will be presented by vaccine group, aggregate IVX-A12, and overall.
- Vaccine groups will be categorized as:
 - Main Trial:
 - 150 µg RSV/ 150 µg hMPV IVX-A12a (unadjuvanted)
 - 150 µg RSV/ 150 µg hMPV IVX-A12d (adjuvanted with MF59®)
 - Placebo
 - Observational Extension Trial:
 - 150 µg RSV/ 150 µg hMPV IVX-A12a (unadjuvanted)
 - Placebo

Aggregate IVX-A12 includes 150 µg RSV/ 150 µg hMPV IVX-A12a (unadjuvanted) and 150 µg RSV/ 150 µg hMPV IVX-A12d (adjuvanted with MF59®).

- All listings will display age, sex, and race.
- Continuous variables will be summarized using the number of observations (n), mean, standard deviation (SD), median, minimum, and maximum. Additionally, quartiles will be provided for continuous variables related to immunogenicity. The same number of decimal places as in the raw data will be presented when reporting minimum and maximum; 1 more decimal place than in the raw data will be presented when reporting mean, median, least squares, and quartiles; and 2 more decimal places than in the raw data will be presented when reporting SD. No more than 3 decimal places will be presented. For confidence intervals (CIs) for mean will be presented with the same decimal places as the mean. For p-values and correlations, 3 decimal places will be presented. P-values <0.001 and >0.999 will be presented as '<0.001' and '>0.999', respectively.
- Descriptive statistics for categorical/qualitative data will include frequency counts and percentages. The total number of subjects in each vaccine group and placebo will be used as the denominator for percentage calculations, unless stated otherwise in the table shell. All percentages will be presented with one decimal point, unless specified otherwise. For percentages equal to 100 will show as 100 rather than 100.0.
- For antibody titer and concentration, antibody concentrations above the lower limit of quantification (LLOQ) are considered accurate and their quantitated values will be reported. In computing geometric means (GM), a titer or concentration reported as < LLOQ will be converted to a value of $\frac{1}{2}$ LLOQ. For calculating a fold-rise, < LLOQ will be converted to $\frac{1}{2}$ LLOQ for a numerator, and < LLOQ will be converted to LLOQ for a denominator when only one of either the numerator or denominator is < LLOQ. If both the numerator and denominator are < LLOQ, then both will be converted in the same way. If >Upper Limit, the upper value will be used to compute GM and fold-rise. Antibody titers and concentrations below the lower limit will be set to $\frac{1}{2}$ LLOQ before performing GMT/GMFR calculations.

This document is confidential.

- For lab results with inexact values, <LLOQ will be converted to ½ LLOQ and >Upper limit will be analyzed as the upper value.
- All statistical analyses will be conducted with the SAS® software package version 9.4 or higher.
- Continuous immunogenicity endpoints will be logarithmically transformed with 2 as base for analysis.

7.1.1. Geometric Mean Titers (GMTs)

Unadjusted GMTs

Unadjusted GMTs and associated 2-sided 95% CI for PPS and EPPS will be calculated for each vaccine group. 95% CIs will be calculated by back transformation of the 95% CI for the mean of the log2 transformed assay results computed using Student's t distribution.

Adjusted GMTs

Adjusted GMTs and associated 2-sided 95% CIs will be obtained using an analysis of covariance (ANCOVA). Unless otherwise noted, for the ANCOVA, log2-transformed titers will be the outcome and vaccine group, age stratification category (age 60-69, age 70-85), and gender as factors and log2-transformed baseline titer as a continuous covariate. Least square means and 95% CIs will be back transformed to provide adjusted GMTs and confidence intervals for each grouping.

For the ANCOVA by age subgroup analyses category (as defined in [Section 7.6](#)), log2-transformed titers will be the outcome and vaccine group, age stratification category, and gender as factors and log2-transformed baseline titer as a continuous covariate. Least square means and 95% CIs will be back transformed to provide adjusted GMTs and confidence intervals for each grouping.

For tertile analyses (and by age subgroup analyses category and tertile), adjusted GMTs and associated 2-sided 95% CIs will be obtained using an analysis of variance (ANOVA). For the ANOVA, log2-transformed titers will be the outcome and vaccine group, age stratification category, and gender will be factors. Least square means and 95% CIs will be back transformed to provide adjusted GMTs and confidence intervals for each grouping.

Note: For the ANCOVA and ANOVA models, the factor of vaccine group consists of 150 µg RSV/ 150 µg hMPV IVX-A12a (unadjuvanted), 150 µg RSV/ 150 µg hMPV IVX-A12d (adjuvanted with MF59®), and Placebo for the PPS.

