4.3. Determination of Sample Size

4.3.1. Main Trial Determination of Sample Size

Sample size for this trial is not based on any formal hypothesis testing. Analyses of safety and immunogenicity will be primarily descriptive in nature. An approximate total of 250 subjects (approximately 100 subjects in each of the IVX-A12 groups and 50 subjects in the placebo group) will be randomized. With 100 subjects in each IVX-A12, there is a 63.4% probability of observing at least 1 subject with an AE if the true incidence of the AE is 1% and 86.7% probability of observing at least 1 subject with an AE if the true incidence of the AE is 2%. The trial will have more than 90% power to detect a difference of 20% or more in seroresponse rate (SRR) or detect a 2-fold increase or more in GMT or GMFR (assuming standard deviation at $0.5 \log_{10}$), between the two IVX-A12 groups (or between the IVX-A12 group and placebo group), with a two-sided type-1 error rate at 0.05.

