Using an ANCOVA, the adjusted GMTs and GMFRs at Day 28 and its 95% CI will be calculated. The outcome variable is Day 28 log2 transformed titers. The factors will include vaccine group, age stratification category, and gender and the covariates will include, log2 transformed baseline titers. Least square means and 95% CIs are back transformed to provide geometric means. To assess whether an adjuvant is required in the formulation to enhance immune responses to IVX-A12, pairwise comparison of the GMT and GMFR least square means from this modeling between non-adjuvant and adjuvant groups will also be displayed. Also, to assess an improvement between the active treatments (IVX-A12a and IVX-A12d) versus placebo, pairwise comparison of the GMT and GMFR least square means from this modeling between IVX-A12a and Placebo and IVX-A12d and Placebo will be displayed. No adjustments for multiplicity will be performed. Data displays will also include boxplots of titers for anti-RSV/A-, RSV/B-, hMPV/A-, and hMPV/B specific NAb ([live-virus assays]) and RSV and hMPV IgG prefusion F protein-specific antibody titers ([ELISAs] at Day 28 for all ages. Log2 transformed titers will be used to create boxplots and back-transformed. The y-axis will be on a log scale. For anti-RSV/A- and RSV/B, the y-axis will display both sets of units.

The above analysis will be repeated as follows:

- By age subgroup analyses category. When using an ANCOVA, the outcome variable is Day 28 log2 transformed titers. The factors will include vaccine group, age stratification category and gender and the covariate is log2 transformed baseline titers;

This document is confidential.

- By baseline tertile; When using an ANOVA, the outcome variable is Day 28 log2 transformed titers. The factors will include vaccine group, age stratification category and gender;
- By age subgroup analyses category and baseline tertile. When using the ANOVA, the factors will include vaccine group, age stratification category, and gender.

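### The single ANCOVA behind the adjuvant and placebo contrasts makes no allowance for unequal residual variance or baseline slope, so its intervals may be modestly miscalibrated; robust standard errors are a cheap safeguard.

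*SAP*

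**What the plan says.** SAP 7.1.1 defines the adjusted GMT through one ANCOVA: "log2-transformed titers will be the outcome and vaccine group, age stratification category (age 60-69, age 70-85), and gender as factors". Baseline enters once for all groups, "and gender as factors and log2-transformed baseline titer as a continuous covariate". A note in the same section makes vaccine group a three-level factor (IVX-A12a, IVX-A12d, placebo).

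SAP 9.1.1.1 reads every comparison off that fit. For the adjuvant question, "pairwise comparison of the GMT and GMFR least square means from this modeling between non-adjuvant and adjuvant groups will also be displayed". For the comparisons with placebo, "pairwise comparison of the GMT and GMFR least square means from this modeling between IVX-A12a and Placebo and IVX-A12d and Placebo will be displayed". SAP 7.1.2 and 7.1.3 carry the method to GMFR and GMR, and 9.1.2 carries it to Days 180 and 365.

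These sections mention no group-specific variance, robust standard error, group-by-baseline term or check of assumptions. A common residual variance and a common slope are therefore the default reading, although the SAP does not say so in words. The unadjusted GMT intervals, by contrast, are t intervals calculated group by group.

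**The concern.** Placebo is aqueous diluent (Protocol 8.1.2). Over 28 days a placebo titer should stay near its own baseline, apart from assay error. Vaccinees add person-to-person variation in response. Equal residual variance is therefore doubtful, and the slope on baseline may differ too.

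If the placebo arm is less variable, it pulls the pooled residual SD below the vaccinees' SD. The interval for IVX-A12d versus IVX-A12a, a comparison that involves no placebo recipient, then becomes too narrow, and the intervals versus placebo become too wide. SAP 9.1.1.1 gives the first contrast as its means of judging whether the formulation needs an adjuvant. In a trial with no formal test, the interval is the main result that a reader takes away.

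**Working it through.** **Inputs from the documents.** Group sizes are "approximately 100 subjects in each of the IVX-A12 groups and 50 subjects in the placebo group" (SAP 4.3.1). One SD, 0.5 log10, serves every comparison (SAP 4.3.1, Protocol 13.4). The target is to "detect a 2-fold increase or more in GMT or GMFR", that is 0.301 log10, at two-sided 0.05.

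**Inputs assumed.** Placebo residual SD, both baseline slopes and the baseline SD (0.4 log10) are not in the documents and were varied or set as shown.

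**The plan's own figure.** The SAP states power above 90%.
- 100 v 100: SE = 0.5 × √(1/100 + 1/100) = 0.0707, and 0.301/0.0707 − 1.96 = 2.30, giving 98.9%.
- 100 v 50: SE = 0.5 × √(1/100 + 1/50) = 0.0866, and 0.301/0.0866 − 1.96 = 1.52, giving 93.5%.

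Both agree with the SAP when the SD is common.

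**Parallel slopes, by formula.** Let r be placebo residual SD divided by vaccine residual SD. Vaccinees are 200/250 = 0.8 of the sample, so the pooled variance is about (0.8 + 0.2r²) times the vaccine variance. The ratio of model SE to true SE is then:
- IVX-A12d v IVX-A12a: √(0.8 + 0.2r²)
- vaccine v placebo: √[(0.8 + 0.2r²) × 0.03 / (0.01 + 0.02r²)]

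For r = 0.4 these are √0.832 = 0.912 and √(0.02496/0.0132) = 1.375. Coverage is 2Φ(1.96 × ratio) − 1.

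| r | A12d v A12a: SE ratio (coverage) | v placebo: SE ratio (coverage) |
|---|---|---|
| 0 (limit) | 0.894 (92.0%) | 1.549 (99.8%) |
| 0.4 | 0.912 (92.6%) | 1.375 (99.3%) |
| 0.6 | 0.934 (93.3%) | 1.233 (98.4%) |
| 0.8 | 0.963 (94.1%) | 1.105 (97.0%) |
| 1.0 | 1.000 (95.0%) | 1.000 (95.0%) |
| 1.25 | 1.055 (96.1%) | 0.899 (92.2%) |

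**Scale of the change.** Take vaccine SD 0.5 and placebo SD 0.2. The pooled SD is √(0.8 × 0.25 + 0.2 × 0.04) = 0.456. The 95% margin for IVX-A12d v IVX-A12a is ×/÷ 10^(1.96 × 0.456 × √0.02) = 1.338 under the model, against 1.376 with the vaccinees' own SD. Versus placebo it is 1.428 under the model, against 1.296.

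**Simulation of the planned model** (100/100/50; baseline, age stratum and gender in the model). In the rows with vaccine SD 0.46, the total vaccine SD is √(0.46² + (0.5 × 0.4)²) = 0.50, which matches the plan's figure. Those rows used 3,000 runs, so Monte Carlo error is about √(0.95 × 0.05/3000) = 0.4 points. The other rows used 6,000 runs.

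| Residual SD, vaccine / placebo | Slopes, vaccine / placebo | Coverage A12d v A12a | Coverage v placebo | With HC3 |
|---|---|---|---|---|
| 0.5 / 0.5 | 0.6 / 0.6 | 95.0% | 94.8% | 95.4%, 95.0% |
| 0.5 / 0.2 | 0.6 / 0.6 | 92.6% | 99.2% | 95.0%, 95.7% |
| 0.46 / 0.10 | 0.5 / 0.95 | 93.0% | 99.1% | see below |
| 0.46 / 0.20 | 0.5 / 0.95 | 93.2% | 98.8% | see below |
| 0.46 / 0.30 | 0.5 / 0.95 | 94.0% | 97.9% | see below |
| 0.5 / 0.2 | 0.5 / 1.0 | 93.2% | 99.0% | 95.5%, 95.7% |
| 0.3 / 0.2 | 0.3 / 1.0 | 95.5% | 95.4% | 95.8%, 95.6% |
| 0.3 / 0.3 | 0.3 / 1.0 | 95.8% | 92.3% | 95.2%, 95.0% |

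In the 0.46 rows the model SE is 5 to 9% too small for the adjuvant contrast and 18 to 38% too large versus placebo. Over all scenarios run, including those rows and one with placebo more variable than vaccine, HC3 coverage lay between 94.5% and 96.2% for both contrasts.

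**Why the slope matters.** Forcing one slope on groups with different slopes adds lack of fit to the residual and raises the pooled SD. A small placebo variance lowers it. The two act in opposite directions, which explains the last two rows.

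**The case against.** A reader might infer that the planned error bars are simply wrong: too narrow for the adjuvant contrast and too wide versus placebo. The documents do not support that. Their only SD is 0.5 log10 for every comparison, and with that SD and parallel slopes the intervals are correct. The quantities that would make them wrong, and fix the direction, are not given. A steeper placebo slope can cancel or reverse the effect. This objection stands, and it is why the point is conditional.

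Nor should the Day 28 sizes be carried to Days 180 and 365. SAP 9.1.2 looks for unrecognised RSV or hMPV infections, which would raise placebo variance. Assuming that 10 to 15% of placebo recipients have an undetected 8-fold rise, coverage was 94.6 to 95.0% for the adjuvant contrast and 95.8 to 96.8% versus placebo, so the problem largely disappears.

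The consequence is also limited. SAP 7.1 states that no formal hypotheses are tested, so reading this as a type I error failure of a confirmatory test would be wrong. Protocol 4.4 records that unadjuvanted IVX-A12a was selected after the Day 28 interim analysis. The SAP also shows per-group unadjusted intervals and boxplots, and its baseline-tertile analyses drop the linear baseline term, so part of any difference in spread or slope would be visible.

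What survives is that the model can err in either direction, the sponsor's stated assumptions cannot tell which, and a remedy that works in both directions is available.

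**Conclusion.** The point holds as a conditional weakness in how precision is reported. If placebo is less variable and the slopes are not too different, nominal 95% intervals cover about 93 to 94% for IVX-A12d versus IVX-A12a and about 98 to 99% versus placebo, for assumed placebo residual SDs of 0.10 to 0.30 log10 against 0.46 in vaccinees. With parallel slopes and placebo no more variable than vaccine, the loss for the adjuvant contrast cannot exceed about 3 points (the 92.0% limit), and the placebo contrasts err on the conservative side.

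This is a cheap improvement of minor importance. Nothing here shows that the choice of formulation would have been different.

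**What to change.** In SAP 7.1.1 and 9.1.1.1, keep the ANCOVA and its point estimates. Report HC3 standard errors, with the resulting intervals and p-values, for the adjusted GMT, GMFR and GMR contrasts in the full per-protocol set at each visit. Add a model with a vaccine-group-by-baseline term, evaluated at the overall mean baseline, as a sensitivity analysis.

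The interaction model should stay a sensitivity analysis. With slopes of 0.3 and 1.0, combining it with HC3 gave 93.2% and 93.9% coverage versus placebo, no better than HC3 on the planned model. Separate variances should not be required in the age-by-tertile cells: with 50 placebo recipients split by tertile and age group (including 80 to 85 years), those estimates could be unstable, and their performance there has not been shown.

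The cost is a sentence or two in the SAP, a little programming and no new data. If placebo is the less variable arm, the adjuvant interval becomes slightly wider (×/÷ 1.376 instead of 1.338 in the illustration). With equal variances and slopes there is no material change.

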7.1.2. Geometric Mean Fold Rise (GMFR)

Unadjusted and adjusted GMFRs will be calculated similarly as the unadjusted and adjusted GMTs.

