7.1.4. Baseline Tertiles

Baseline tertiles are defined as follows: first tertile is <=33.3rd percentile, second tertile is >33.3rd - <=66.7th percentile, and third tertile is >66.7th percentile.

When summarizing by age subgroup category, baseline tertiles are defined as follows: first tertile is <=33.3rd percentile, second tertile is >33.3rd - <=66.7th percentile, and third tertile is >66.7th percentile by total arm within each age subgroup category.

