9.1.1.2. Analysis of Subjects with a ≥ 4 -Fold Increase

The proportion of subjects with a ≥ 4 -fold increase in serum anti-RSV/A-, RSV/B-, hMPV/A-, hMPV/B-specific NAb (live-virus assays), RSV and hMPV IgG prefusion F protein-specific antibody titers will be calculated at Day 28 and summarized by vaccine group for each of the following: RSV-A, RSV-B, both RSV strains, either RSV strains, hMPV-A, hMPV-B, both hMPV strains, either hMPV strains, RSV and hMPV IgG prefusion F protein-specific antibody titers. The 95% CI of the difference in proportion of subjects with a ≥ 4 -fold increase in serum anti-RSV/A-, RSV/B-, hMPV/A-, hMPV/B-specific NAb (live-virus assays), RSV and hMPV IgG prefusion F protein-specific antibody titers between vaccine groups with and without adjuvant and IVX-A12a versus Placebo and IVX-A12d versus Placebo will be computed using Wilson's score method. Logistic regression models will be used to further describe the IVX-A12d response to vaccination when compared to IVX-A12a. Also, logistic regression models will be used to describe the response of IVX-A12a versus Placebo and the response of IVX-A12d versus Placebo. The outcome variable is binary (≥ 4 -fold increase or no ≥ 4 -fold increase). Vaccine group, log2 transformed baseline NAb titer, age stratification category, and gender are included as explanatory variables.

The ≥ 4 -fold increase analyses will be repeated for the following:

- By vaccine group and age subgroup analyses category. For the logistic regression models, vaccine group, log2 transformed baseline titer, age stratification category and gender are included as the explanatory variables;
- By vaccine group and baseline tertile; For the logistic regression models, vaccine group, age stratification category and gender are included as the explanatory variables;
- By vaccine group and age subgroup analyses and baseline tertile. For the logistic regression models, vaccine group, age stratification category and gender are included as the explanatory variables.

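### The whole-population baseline-tertile GMT and GMFR models omit the continuous baseline titer, so outer-tertile group contrasts are somewhat less precise than they need to be

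*SAP*

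**What the plan says.** SAP 7.1.1 fits the main and the age-subgroup GMT models as ANCOVAs with "log2-transformed baseline titer as a continuous covariate". It then switches to a model without baseline, both for the tertiles and for age category crossed with tertile: "For the ANOVA, log2-transformed titers will be the outcome and vaccine group, age stratification category, and gender will be factors". Tertile is not a factor in that model, so I read it as fitted separately within each tertile.

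SAP 7.1.4 sets the cut points: "first tertile is <=33.3rd percentile, second tertile is >33.3rd - <=66.7th percentile, and third tertile is >66.7th percentile". The lowest and highest groups are therefore unbounded on one side.

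SAP 9.1.1.1 repeats the choice for Day 28: "By baseline tertile; When using an ANOVA, the outcome variable is Day 28 log2 transformed titers". SAP 9.1.2 carries the tertile GMT and GMFR analyses to Days 180 and 365. For fold rise, SAP 7.1.2 says "Unadjusted and adjusted GMFRs will be calculated similarly as the unadjusted and adjusted GMTs".

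The contrasts at issue are those in SAP 9.1.1.1, where "pairwise comparison of the GMT and GMFR least square means from this modeling between non-adjuvant and adjuvant groups will also be displayed", together with each active group against placebo. All are then repeated by tertile. The tertile logistic models in SAP 9.1.1.2 leave baseline out as well: "By vaccine group and baseline tertile; For the logistic regression models, vaccine group, age stratification category and gender are included as the explanatory variables".

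Protocol 13.1.3 names one adjusted model, an ANCOVA with log baseline titer, age group and treatment group. SAP section 12 records the added gender factor and the age-subgroup repeats, but not the ANOVA. No reason for the switch is given.

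**The concern.** Belonging to a tertile does not fix a subject's baseline titer. Within an outer tertile baseline still varies, and to the extent that it predicts the later titer, leaving it out puts avoidable variation into the residual. With about 33, 33 and 17 subjects per group in a tertile, there is little precision to spare.

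There is a second, visible consequence. When baseline is in the model, the GMT and GMFR contrasts between two groups are the same number. Without it they differ by whatever baseline difference chance has left between the groups in that tertile. Two tables both labelled as adjusted could then give different-looking answers to the adjuvant question within one tertile.

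**Working it through.** **Inputs from the documents.** Groups of 100, 100 and 50; SD 0.5 log10 for GMT or GMFR; a 2-fold difference (log10 2 = 0.301); two-sided alpha 0.05 (Protocol 13.4, SAP 4.3.1).

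**Assumptions.** Bivariate normal log titers with equal SDs of 0.5, no dropout, tertile group sizes 33/33/17, and a baseline to Day 28 correlation ρ of 0.3 to 0.7. The adjusted GMFR model is taken to have log2 fold rise as its outcome.

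**The plan's own figure.** More than 90% power for a 2-fold difference reproduces: 98.9% for 100 vs 100 and 93.5% for 100 vs 50. These are whole-population figures.

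**A reference value for ρ.** If baseline, Day 28 titer and log fold rise all have SD 0.5, then 0.25 = 0.25 + 0.25 − 2ρ(0.25), so ρ = 0.5.

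**Baseline variance left within a tertile (v).** From the truncated normal, v = 0.280 in each outer tertile and 0.060 in the middle. The average is (0.280 + 0.060 + 0.280)/3 = 0.207, so the split itself removes about 79%.

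**Loss of precision.** The residual variance ratio, without baseline to with it, is:

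- GMT: (1 − ρ² + ρ²v)/(1 − ρ²). At ρ = 0.5 in an outer tertile: (0.75 + 0.25 × 0.280)/0.75 = 0.82/0.75 = 1.093, and √1.093 = 1.046.
- GMFR: 1 + v(1 − ρ)/(1 + ρ). At ρ = 0.5: 1 + 0.280 × 0.5/1.5 = 1.093, the same value.

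| ρ | GMT SE ratio, outer | GMT SE ratio, middle | GMFR SE ratio, outer |
|---|---|---|---|
| 0.3 | 1.014 | 1.003 | 1.073 |
| 0.5 | 1.046 | 1.010 | 1.046 |
| 0.7 | 1.127 | 1.029 | 1.024 |

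The GMT loss grows with ρ and the GMFR loss shrinks.

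**Simulation of the SAP's models** (three groups, age stratum, gender, 250 subjects), which charges for the extra degree of freedom. For the outer-tertile GMT contrast the mean CI width ratios are 1.01, 1.04 and 1.12. The median narrowing from adding baseline is about 0%, 3% and 10%. In the middle tertile the width ratios are 1.00, 1.00 and 1.02. ANOVA coverage was 94–96%, with no material bias.

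**Power** for a 2-fold difference, 33 vs 33, outer tertile, normal approximation without the degree-of-freedom cost: 71.5% rises to 72.7% (ρ = 0.3), 77.1% to 80.6% (0.5), and 86.0% to 92.8% (0.7).

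**GMT against GMFR.** Without baseline in the model, log GMFR contrast = log GMT contrast − baseline contrast. In an outer tertile the SE of that baseline contrast is 0.5 × √0.280 × √(1/33 + 1/33) = 0.0651 log10. At its 95% limit the two ratios differ by a factor of 10^(1.96 × 0.0651) = 1.34. For 33 vs 17 the SE is 0.0790 and the factor 1.43. With baseline in the model the group coefficients are identical, because subtracting baseline from the outcome only lowers the slope by 1.

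**Sparse cells.** In an illustrative 30-subject age subgroup, about 10 per tertile, the ANOVA/ANCOVA width ratio is 0.83 to 0.94. There the extra term widens the interval.

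**The case against.** The strongest reply is that stratifying on baseline is already a form of adjustment. It removes about 79% of the baseline variance, and what remains matters only in the outer tertiles. These are subgroup displays in a trial with no formal hypotheses and no multiplicity adjustment. The main Day 28 ANCOVA already carries continuous baseline, and Protocol 4.4 says the unadjuvanted formulation was chosen after the Day 28 interim analysis. All of that stands, and it keeps this point small.

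A reader might go further and infer that the tertile contrasts are biased by baseline imbalance. They are not. Tertile is fixed before randomization, so any imbalance within it arises by chance, and the ANOVA interval already allows for it. Imbalance and lost precision are one effect, not two.

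A reader might also infer that every model without baseline should regain it. That does not follow:

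- In the age-by-tertile cells, where tertiles are recut within each age category (including 80–85), the term can cost precision.
- In the logistic models the variance formula does not apply. A further covariate changes the odds ratio being estimated, and no gain has been shown.

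Finally, agreement of GMT and GMFR is not complete even with the covariate. SAP 7.1 treats values below the LLOQ differently in a geometric mean and in a fold-rise denominator, and any such baseline values fall in the lowest tertile.

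**Conclusion.** The point holds for the whole-population tertile-level linear models at Days 28, 180 and 365, and only there. In the outer tertiles, GMT intervals at Day 28 would typically be 0–10% narrower with baseline included, over assumed correlations of 0.3 to 0.7, and about 3% narrower at 0.5. The middle tertile shows essentially no difference. Displayed GMT and GMFR ratios within an outer tertile can differ by up to about 1.34-fold (active vs active) or 1.43-fold (active vs placebo) at the 95% limit of chance imbalance.

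The sizes rest on normal log titers, equal SDs of 0.5 log10 and full follow-up. The documents state no baseline to Day 28 correlation and none for the later visits. Neither the validity of the ANOVA intervals nor the primary Day 28 comparison is in question. This is a modest, inexpensive gain in precision and consistency, plus an unlisted departure from the protocol's model.

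**What to change.** - In SAP 7.1.1, with matching wording in 9.1.1.1 and 9.1.2, keep log2 baseline titer of the same assay as a continuous covariate in the whole-population tertile models for GMT and GMFR.
- Leave the age-by-tertile models without it, and say that this is because the cells are sparse.
- Do not change the tertile logistic models on grounds of precision.
- In SAP section 12, list any ANOVA that remains as a departure from the protocol's ANCOVA, with the reason.

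The cost is one degree of freedom per model, and the reprogramming and revalidation of the affected tertile outputs. The covariate is already in the data and in the main model. If the sponsor prefers the ANOVA throughout, the section 12 entry is the minimum, with a table note that GMT and GMFR contrasts within a tertile may differ through chance baseline differences.
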